5.4 Randomization

Participants will be stratified to three groups (Obesity, Obesity HTN, and Obesity DM) and will be randomly assigned to treatment or control group with a 1:1.5 allocation per a computer generated randomization using variable block randomization.

Participants will be notified of their randomization assignment on the day of the randomization visit. Participants randomized to the control group will proceed to an appointment with the dietitian for their Week 1 visit on the day of randomization. Participants randomized to the treatment group will proceed to a brief visit with the dietitian to review the post-op liquid diet, and the ESG will be scheduled within 30 days of randomization. Participants of child-bearing potential will be required to have a pregnancy test within 7 days of the scheduled ESG.

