7 STATISTICAL ANALYSIS

7.1 Power and Sample Size

The primary endpoint for power and sample size is %EWL at 12 months. The null hypothesis is no difference in mean %EWL between ESG and LS randomized arms ($H_0: \mu_t = \mu_c$ where μ_t is the average %EWL in the ESG group and μ_c is average %EWL in the LS group). We will perform a two-sided hypothesis test at alpha level 0.05 (alternative hypothesis $H_a: \mu_t \neq \mu_c$) Based on the published literature with the ESG technique a conservative presumption is 25% EWL in the ESG arm with a standard deviation (SD) of 30% at 12 months compared to 10% EWL on LS alone with SD of 5%. We plan a 1:1.5 randomization scheme that allocates 3 patients to LS for every 2 to ESG at the time of randomization. Based on a two-sample t-test with unequal variances and two-sided alpha=0.05, we would have 80% power to detect a difference of 15% in average %EWL between groups with 34 patients allocated to ESG and 51 randomized to LS. 90% power would require group sizes of 45 and 68, respectively. To allow for dropout, and more importantly, to power exploratory aims for obesity comorbidity subgroups, we propose the initial randomization of 200 patients – 80 to ESG and 120 to LS.

120 subjects are initially randomized to LS in level 1. Of these, we anticipate up to 20% will achieve a successful decrease of $\geq 25\%$ in %EWL through LS alone at 12 months. Further, we anticipate up to 20% may be lost to follow up or drop out prior to 12 month follow up. Thus, we anticipate at least 77 ($120 * 0.8 * 0.8$) subjects to continue to level 2 and be offered ESG. We will test the one-sample hypothesis (non-randomized) that of those offered ESG at 12 months, average change in %EWL will be at least 10%. Based on a one-sample t-test with two-sided alpha=0.05 and standard deviation at 24 months of 30%, 70 subjects completing ESG would have 98% power to detect an effect of 25% reduction in %EWL.

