7.2.1 Primary Aim

The primary outcome is %EWL at 12 months assessed in the two randomized arms. A hierarchical linear regression model will be fitted to post-randomization %EWL measurements, planned for 11 post-randomization timepoints through 12 months. Post-randomization outcomes will be modeled as a function of discrete visit (instead of assuming a linear or other functional form of time since randomization) and treatment indicator variables. Models will also adjust for age, sex, baseline BMI, HTN, and DM status to reduce residual variation and improve power. The primary outcome comparison at 12 months is estimated from a linear combination of treatment and time indicators. A spatial autocorrelation covariance structure will be used.

Assumptions for normality of residuals and homoscedastic variance will be assessed; hierarchical median regression (Geraci and Bottai, 2014) will be considered under significant violations.

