7.2.2 Secondary Aims

Continuous secondary outcomes, including change in systolic and diastolic blood pressure and change in HbA1c, QOL questionnaires such as the SF-36, PHQ-9, and eating behavior scores will be compared between treatment arms using ANCOVA with adjustment for the same variables specified in the primary analysis.

Binary outcomes, including proportion with $\geq 25\%$ reduction in %EWL and incidence of esophagitis will be compared between treatment arms by Pearson Chi-square test.

Among patients randomized to the treatment ESG group, the association between the durability of plication at repeat endoscopy (score ≥ 1 on EGD grading system) and number of sutures required for re-tightening with change in EWL from 12 months to 24 months will be assessed using linear regression with adjustment for BMI, %EWL between randomization and 12 month follow up, HTN status, and DM status. This is an observational comparison.

Among patients randomized to the control LS arm, the percent EWL from the 12 month assessment to the 24 month assessment will be measured. This percentage will be compared to percent EWL in the same group with lifestyle intervention only in the first 12 months using a one sample t-test.

Among all subjects, %EWL will be compared at 24 months between initial and delayed ESG. However, this is not considered a comparison of randomized arms as follow up is not continued for patients with $\geq 25\%$ EWL from LS at 12 months.

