7.4 Randomization and Data Collection

Stratified block randomization schedules will be uploaded to REDCap, with strata defined by HTN and DM status. Data will be collected in REDCap data collection forms.

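### The weight-based responder endpoints get an unadjusted chi-square while the rest of the plan adjusts for covariates: a valid test, but slightly inefficient, inconsistent, and without a rule for a missing week-52 weight

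*Combined protocol and SAP*

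**What the plan says.** Section 7.2.2 (Secondary Aims) treats binary outcomes as one class. It names the 25% EWL proportion and esophagitis as examples and ends: "incidence of esophagitis will be compared between treatment arms by Pearson Chi-square test". It mentions no covariates, strata or missing outcomes. The >5% and >10% TBWL proportions in section 4.2.1 are also binary, so they fall under the same sentence.

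The other comparisons of randomized arms are adjusted. Section 7.2.1 states: "Models will also adjust for age, sex, baseline BMI, HTN, and DM status to reduce residual variation and improve power". Continuous secondary outcomes are compared "using ANCOVA with adjustment for the same variables specified in the primary analysis". Section 5.4 stratifies randomization into three groups (obesity, obesity with HTN, obesity with DM), and section 7.4 describes the schedules "with strata defined by HTN and DM status".

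Section 7.3 gives a missing-at-random (MAR) approach for the primary hierarchical model. It adds a conditional sensitivity analysis, with multiple imputation, for patients who leave before the intervention or before the first follow-up visit. Section 7.2.3 makes modified intention-to-treat the main approach to efficacy and keeps treated patients in the analysis whether or not they attend follow-up.

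**The concern.** The plan's own reason for adjusting, less residual variation and more power, applies equally to a responder endpoint built from the same weights. Baseline BMI matters in particular because it enters the definition. With 25 as ideal BMI (section 2.3), reaching 25% EWL takes a larger share of body weight the heavier the patient is at baseline. BMI is not a stratification factor.

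The second part is missing outcomes. A patient who leaves at week 36, say, contributes to the primary model but has no defined status on the 25% EWL endpoint, which is listed first among the secondaries. In an open-label trial that rule should be fixed before the data are seen.

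**Working it through.** **1. The plan's own figures.** Section 7.1 sets the test ("We will perform a two-sided hypothesis test at alpha level 0.05") and assumes "25% EWL in the ESG arm with a standard deviation (SD) of 30% at 12 months compared to 10% EWL on LS alone", with SD 5% on lifestyle (LS). Welch t-test:
- 34/51: SE = sqrt(30²/34 + 5²/51) = 5.19; noncentrality 15/5.19 = 2.89; df 34.2; power 80.1% (stated 80%).
- 45/68: SE = sqrt(30²/45 + 5²/68) = 4.51; noncentrality 3.32; df 45.6; power 90.2% (stated 90%).

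Both reproduce. The plan states no power for any binary endpoint.

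**2. Chi-square power for 25% EWL.** A normal distribution with mean 25 puts 50% of ESG patients at or above 25%. For LS, section 7.1 anticipates up to 20%. (Mean 10 and SD 5 would give 1 − Φ(3) = 0.13%; 20% is the less favourable input.)

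Power = Φ((d − 1.96·se0)/se1), with pooled se0 and unpooled se1:
- 50% v 20%, 80/120: (0.30 − 1.96 × 0.0673)/0.0668 = 2.52; power 99.4%.
- 50% v 20%, 64/96 (20% lost in both arms, an assumption): (0.30 − 1.96 × 0.0753)/0.0747 = 2.04; power 97.9%.
- 40% v 20%: 86.6% at 80/120 and 78.5% at 64/96.

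**3. Link with BMI.** Required TBWL = 25 × (BMI − 25)/BMI: 4.2% at BMI 30 and 9.4% at BMI 40. The planned 15-point EWL difference is 15 × (BMI − 25)/BMI in TBWL: 2.5 points at BMI 30, 4.3 at 35 and 5.6 at 40.

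**4. Gain from adjusting for BMI.** Simulated trials of 80/120, with assumed BMI uniform on 30–40, TBWL unrelated to BMI and TBWL SD 4–5%:

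| TBWL effect | SD | SE of risk difference, unadjusted v adjusted | Power, chi-square v adjusted |
|---|---|---|---|
| 1.5 points | 4 | 0.059 v 0.057 | 41.5% v 44.2% |
| 2 points | 4 | 0.066 v 0.063 | 67.7% v 69.2% |
| 4.3 points | 4 | – | 100% v 100% |
| 4.3 points | 5 | – | 99.4% v 99.7% |

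The first two rows use 600 trials each, so the Monte Carlo SE of each power figure is about 2 points. Separate runs at modest effects gave 43.8% v 45.7% and 65.9% v 67.7%, and at the planned effect 99.4% v 99.5%.

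**5. Error rate, and stronger prognostic effects.** 4,000 trials per row; assumed strata of 50/75/75, LS response about 20%, conditional log odds ratio 0.8. Order: Pearson / Cochran-Mantel-Haenszel (CMH) / adjusted logistic.

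| Assumed prognostic strength | Type I error | Power |
|---|---|---|
| None | 0.050 / 0.050 / 0.049 | 0.71 / 0.70 / 0.70 |
| Moderate | 0.052 / 0.054 / 0.055 | 0.63 / 0.63 / 0.66 |
| Strong | 0.046 / 0.052 / 0.053 | 0.50 / 0.53 / 0.61 |
| Very strong | 0.034 / 0.052 / 0.050 | 0.44 / 0.51 / 0.56 |

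Pearson is never materially above 5%. The large gains need strong prognostic effects, for which the documents give no evidence.

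**6. Missing week-52 status.** True rates 50% v 20%:
- 20% missing in each arm (assumed): completers 50 − 20 = 30 points; missing counted as failure 40 − 16 = 24; worst case for ESG 40 − (16 + 20) = 4.
- 20% missing in LS only: completers 30; missing counted as failure 50 − 16 = 34; worst case 50 − 36 = 14.

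The rule moves the estimate more than adjustment does. Counting missing as failure is not always conservative: it widens the difference when more LS patients are lost.

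**The case against.** The strongest reply is that this is preference, not error. An unadjusted chi-square is valid under stratified randomization, adjustment in the primary model is there for efficiency, and at the planning rates nothing is gained. That largely stands. The modest-effect gains in step 4 also come from TBWL effects of 1.5 and 2 points, below the 2.5 points that the planned difference implies even at BMI 30. What survives is the inconsistency and the missing classification rule, both curable at almost no cost.

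A reader might infer more than the documents support:

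- **That the chi-square inflates type I error.** It does not; with strongly prognostic strata it becomes conservative (step 5).
- **That the plan prescribes a completers-only test on about 160 of 200 patients.** Section 7.2.2 does not say so, and section 7.2.3 points towards keeping patients in; the plan is silent on how to classify them. The loss of up to 20% is stated for LS only and as an upper bound. As written it leaves at least 200 − 0.2 × 120 = 176. No ESG loss rate is given.
- **That the continuous secondaries already handle missing outcomes.** The ANCOVA has no missing-data rule either. The contrast with it holds for covariates and strata only.
- **That adjustment would mend the esophagitis comparison.** The Level 1 control schedule in section 5.6 marks no endoscopy. Section 4.1 has patients who received ESG re-examined at about 52 weeks, while section 5.5.1.1.2 exempts those above 25% EWL. A covariate model cannot supply outcomes that are not scheduled.

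Medication-reduction endpoints concern only patients on those drugs, so stratifying by comorbidity group would add little there.

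**Conclusion.** The point holds as a minor improvement for the weight-based responder endpoints (25% EWL, 5% and 10% TBWL). It concerns efficiency, consistency and an unstated missing-outcome rule; it is not a validity error. The expected gain from adjustment is about 1 to 3 power points at modest effects and near zero at the planned effect. This rests on an assumed BMI distribution and TBWL spread, and on proportional weight loss being unrelated to BMI; the documents give none of these. Larger gains appear only under stronger prognostic effects than the documents support. The missing-outcome rule is the part that could visibly move the reported difference, by an amount that depends on loss in each arm. Esophagitis lies outside this point.

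**What to change.** In section 7.2.2, replace the chi-square for the weight-based responder endpoints with logistic regression on treatment and the section 7.2.1 covariates, coding HTN and DM so that the randomization strata are represented. Report the standardized risk difference with 95% CI. At the planning rates about 0.5 × 80 + 0.2 × 120 = 64 responders would support the six terms (treatment, age, sex, BMI, HTN, DM). If LS responders prove very rare, a fallback named in advance is needed, such as penalized logistic regression or CMH by stratum.

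For patients without a week-52 weight, multiply impute it from the earlier visits under the primary model's MAR assumption, then dichotomize. Add a sensitivity analysis counting missing as non-response, read together with the loss in each arm.

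Handle esophagitis separately: sections 4.1, 5.5.1.1.2, 5.6 and 7.2.2 must be reconciled on who has a 12-month endoscopy and which groups can be compared.

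Cost for the weight endpoints: a paragraph of SAP text and modest programming. Weights and covariates are already collected; no visit or sample-size change is needed.

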4 STUDY DESIGN

4.1 General Description

This study is a multi-center, randomized, open-label clinical trial evaluating the efficacy and safety of ESG as an adjunct to life-style intervention for weight loss and improvement in obesity-related co-morbidities compared to lifestyle intervention alone in participants with a BMI ≥ 30 and ≤ 40 kg/m² who have failed to achieve and maintain weight loss with a non-surgical program.

Participants will be recruited from outpatient clinical weight loss clinics and from study-related institutional review board (IRB) approved advertisements. The cohort will include nor more than 50 patients without at least one of a) hypertension (HTN) on one or more anti-hypertensive medications or b) type II diabetes mellitus (DM) on oral agents only with HbA1c ≤ 9 . Enrollment will be tracked continuously and enrollment closed to non-DM, non-HTN patients after meeting the target for that group.

Two hundred eligible participants will be stratified into three groups (obesity, obesity-hypertension, and obesity-diabetes) and then block-randomized 1 to 1.5 to treatment (80 participants) and control (120 participants) groups alone as depicted in the diagram on page 16. All treatment group participants will undergo endoscopy and those without endoscopic contraindications will undergo the ESG. All control subjects will follow a low-calorie, healthy lifestyle intervention only for 12 months. After 12 months of lifestyle intervention, eligible control participants will crossover to receive the ESG. Those who had the ESG will undergo a repeat upper endoscopy at 52 weeks +- 4 weeks to evaluate the durability of the plications and re-tighten the ESG if needed with continued follow-up for 12 additional months.

The study will have two levels:

1. Level 1: the randomized study phase with primary outcomes for both groups evaluated at 12 months
2. Level 2: the crossover, non-randomized study phase with outcomes for a) the initial treatment group at 24 months post ESG (12 months after the re-tightening procedure) b) for the controlled cross-over group evaluated at 12 months after ESG

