4.2 Endpoints

4.2.1 Effectiveness

Primary:

- % EWL at 12 months from randomization by randomized arm measured at the week 52 visit. The null hypothesis is no difference in mean %EWL between randomized arms.

Secondary:

- Proportion with $\geq 25\%$ EWL at 12 months by randomized arm
- Change in hypertension in the ESG group compared to LS only

- Proportion of patients off or with reduction in their antihypertensive medications in the randomized control arm compared to lifestyle control at 12 months
- Change in systolic and diastolic blood pressure in the randomized arm compared to lifestyle control at 12 months
- Comparing diastolic and systolic blood pressures as continuous variables 12 months after ESG (compared to baseline) in the entire cohort that received ESG both in the randomized and cross-over segments of the trial
- Change in type II diabetes in the ESG groups compared to LS only
 - Proportion of patients off or with reduction in their diabetes medications in the randomized arm compared to lifestyle control at 12 months
 - Change in HgbA1c in the randomized arm compared to lifestyle control at 12 months
 - Comparing HgbA1c as a continues variable 12 months after ESG (compared to before) in the entire cohort that received ESG both in the randomized and cross-over segments of the trial.
- %TBWL in the ESG group compared to LS only
- % of patients in the ESG group achieving > 5% TBWL compared to LS only
- % of patients in the ESG group achieving > 10% TBWL compared to LS only
- Durability of the plication evaluated by endoscopy at 12 months (level 1) and effectiveness of re-tightening procedure performed at 12 months (level 1) in maintaining and / or enhancing weight loss at 24 months. Durability of the plication and procedure is defined as greater than 70% of the cohort undergoing repeat endoscopy achieving a score of ≥ 1 out of 3 prior to re-tightening (Grading system and evaluation in appendix). Efficacy of re-tightening is defined as $\geq 50\%$ of the cohort undergoing the re-tightening maintaining or losing weight compared to the re-tightening weight at 12 months after the re-tightening procedure.
- Incidence of esophagitis at repeat endoscopy at 12 months (level 1). (LA grading system in form in appendix)
- Changes in quality of life assessed using standard validated questionnaires (IWQOL-lite and SF-36)
- Changes in depression assessed using PHQ-9 questionnaire

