5.3 Screening and Eligibility Assessment

Screening will be conducted by the investigator or the co-investigator and documented on the Investigator delegated/medically qualified team member intake form (conventionally known as PI Intake Form) (Appendix A) and Screening Labs form (Appendix B). Screening must occur no more than 45 days prior to randomization.

Screening will include the following:

1. Sign informed consent form
2. Screening exam and intake by the investigator or co-investigator
3. Height, weight and BMI; waist and hip circumference; vital signs (blood pressure and pulse)
4. Dietary screening intake and approval
5. Laboratory tests (after 8 hours fasting)

- **CBC:** Hgb, Hct, WBC, MCV, platelets
- **Chemistry panel:** sodium, potassium, chloride, CO₂, BUN, creatinine, fasting glucose, insulin, SGOT/AST, SGPT/ALT, alkaline phosphatase, total bilirubin, direct bilirubin, total protein, albumin, fasting lipids profile (total cholesterol, triglyceride, LDL cholesterol, HDL cholesterol) Fe/TIBC, iron, B12, 25-Hydroxy Vitamin D, TSH, total Ghrelin level (only if available at participating institution), C-reactive protein.
- **Coag:** Pro Time or INR, PTT
- **PYY-1, GLP-1, Total Ghrelin** pending sites' availability to analyze
- **Urinalysis**
- **HgbA1C**
- **H. Pylori Breath Test.** **Patients with a positive h-pylori breath test will be treated and eradication must be confirmed with a stool antigen after treatment and prior to randomization**
- **EKG** for patients 50 years old or older
- **Urine pregnancy test** for women of child bearing potential

6. Questionnaires
7. Psychological evaluation and approval: Study psychologists will use their standard clinical evaluations for bariatric interventions.

Within one week of completion of the screening tests, the PI will review the results and determine the participant's eligibility. The center will inform the participant of their screening results within 10 days of completing testing. Any abnormal lab results will be communicated to the participant and they will be required to notify their primary care provider for any further action that may be necessary. All potential participants who qualify for randomization based on the initial screening assessments will return for a randomization visit where participants will have the chance to review any questions with the study staff, as well as a recap of the follow-up schedule, and they will then receive their randomization assignment.

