5.5.1.1.2 Treatment Group

ESG is an endoluminal procedure similar to sleeve gastrectomy targeting the shape of the stomach. The targeted shape is tubular gastric body with a small pouch in the fundus. A step-by-step video circulated to all sites and a mandate to have the proctor present for the first case were done to ensure conformity to the technique. The same expert endoscopist will proctor all sites. In general, the technique involves 7-9 bites in a running O shaped pattern that is repeated 4-5 times in the stomach to achieve the desired shape. Proximally, it might be difficult to do the O sequence; thus, the operator can do triangular 3-4 bites interrupted suturing sequence. Each O sequence can be enforced by a layer of triangular interrupted suture. All bites are intended to be full thickness with the aid of tissue helix. The re-enforcing bites can be submucosal. The sequence is staggered to avoid gaps. In general, sutures used is limited to 10. ESG narrows the stomach axially and reduce its length longitudinally.

Participants assigned to the treatment group will report to the procedure suite within 30 days of randomization. Participants of child-bearing potential will be required to have a pregnancy test within 7 days of the scheduled ESG. Participants taking medications for hypertension and/or type II diabetes will be instructed to notify their prescribing physician of their procedure and to discuss any necessary medication changes for the post-op period.

The ESG is done in the outpatient setting. Within two hours prior to ESG, IV access will be obtained, IV hydration initiated, and a transdermal scopolamine patch placed for patients 50 years of age or younger (this will be removed in 24 to 48 hours after the procedure).

Prior to ESG, a standard upper endoscopy is performed to rule out any contraindicating findings. All ESG procedures will be done under general anesthesia with endotracheal intubation and utilizing CO₂ insufflation. During the procedure, IV hydration will be continued and patients will be given the following: one dose of IV antibiotics (Zosyn, Ceftriaxone, or Ciprofloxacin), 8mg of IV Zofran, and 8mg of Decadron. A minimum of two liters of IV hydration (either normal saline or lactate ringers) should be administered in the perioperative recovery period before discharge. Sequential compression devices (SCDs) will be used perioperatively to decrease the risk of deep vein thrombosis (DVT) and pulmonary embolism (PE).

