	Enrollment; Screening/ Baseline	Randomization / Week 1 visit	Weeks 4, 8	Week 12	Weeks 16, 20	Week 24 (6 month)	Weeks 30, 36, 42, 48	Week 52 (Final Year 1 visit), re-screen for crossover to ESG	Unscheduled Visit
Visit Number	-1	1	2,3	4	5,6	7	8,9,10,11,	12	
Informed consent	X								
Complete Physical Exam (CPE) by Investigator or Investigator delegated / medically qualified team member	X			X		X	X	X	X
Investigator or Investigator delegated/medically qualified team member exam		X ⁺⁺	X	X	X	X	X	X	X
EKG if (> 50 yo)	X							X	
Formal nutritional assessment	X								
Formal psychology evaluation	X								
Pregnancy test (females of childbearing potential only)	X								
Laboratory tests, H-pylori breath testing (baseline only)* *	X							X	
Questionnaires#	X			X		X		X	
Inclusion/exclusion criteria	X							X	
Endoscopy / Procedure									
Procedure Assessment Form									
GERD Questionnaire + Activity Assessment Form	X	X	X	X	X	X	X	X	
Weight, BMI/height, Waist and Hip Circumference Form	X	X	X	X	X	X	X	X	X
Vital Signs Form	X	X	X	X	X	X	X	X	X
Adverse Events Form		X	X	X	X	X	X	X	X
Medications Form##	X	X	X	X	X	X	X	X	X
Post-enrollment Nutrition / Exercise / satiety counseling and assessment		X	X	X	X	X	X	X	
Randomization to ESG vs. LS ⁺		X							
Subject Satisfaction Questionnaire (control phase)								X	

** Electrolytes, Creatinine, CBC, Iron, TIBC, B12, 25-hydroxy Vitamin D, TSH, HgA1c, fasting blood sugar and insulin, PTT, fasting lipids profile (total cholesterol, LDL, HDL, and Triglyceride), ALT, AST, ALK-P, total bilirubin, direct bilirubin, BUN, total protein, albumin, CRP, urinalysis; also include PYY-1, GLP-1 and total Ghrelin pending sites' availability to analyze

Eating disorder questionnaire + hospital anxiety and depression questionnaires (only at base-line), IWFQOL-Lite, SF36, PHQ9, Pittsburgh Sleep Quality Index (PSQI), Three factor eating questionnaire (TFEQ)

Record all medications including dose and frequency; especially diabetes and blood pressure medication.

+ LS start with the week 1 visit with no transitional diet.

++ Required only for Week 1 visit

5.6.1.1.4 Schedule of Events for Control Group, Crossover in Year 2, Level 2

[figure not shown]
TABLE 3. MERIT SCHEDULE OF EVENTS (Year 2, Level 2, Control Group, cross-over 120 patients)									
	ESG Procedure	Post-Op Phone Call	Weeks 1, 4, 8	Week 12	Weeks 16, 20	Week 24 (6 month)	Weeks 30, 36, 42, 48	Week 52 (Final Year 1 visit)	Unscheduled Visit
Visit Number	0	-	1,2,3	4	5,6	7	8,9,10,11	12	

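### The between-arm chi-square for esophagitis has no control data, because no control has a scheduled endoscopy before crossover; the ESG patients who are re-scoped are a selected group as well

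*Combined protocol and SAP*

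**What the plan says.** **The test and the endpoint.** Among the binary outcomes, section 7.2.2 says that "incidence of esophagitis will be compared between treatment arms by Pearson Chi-square test". Section 4.2.1 lists the endpoint as "Incidence of esophagitis at repeat endoscopy at 12 months (level 1"), graded by the LA system.

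**Controls.** Section 4.1: "All control subjects will follow a low-calorie, healthy lifestyle intervention only for 12 months". The list in section 5.3 that opens "Screening will include the following" contains no endoscopy. In the control Year 1 schedule (5.6.1.1.3) the row "Endoscopy / Procedure" is empty in every column, screening and week 52 included. The first scope a control can have is the one before crossover ESG; section 5.5.1.1.2 says "Prior to ESG, a standard upper endoscopy is performed to rule out any contraindicating findings". Section 4.1 calls Level 2 "the crossover, non-randomized study phase".

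**ESG patients.** Section 4.1: "All treatment group participants will undergo endoscopy and those without endoscopic contraindications will undergo the ESG". For the repeat scope the sections differ:

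- Section 4.1 re-scopes patients who had the ESG, at 52 weeks plus or minus 4.
- Section 5.5.1.1.2 spares patients above 25% EWL and scopes the rest at 52 to 60 weeks.
- The Year 2 treatment schedule (5.6.1.1.2) marks an endoscopy only in the retightening column, for qualifying patients at weeks 52 to 60.

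**Durability.** Section 4.2.1 sets the criterion at more than 70% of re-endoscoped patients scoring at least 1 of 3.

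**The concern.** A two-arm test needs an outcome in both arms. Here the outcome can only be seen by endoscopy, and one arm has none scheduled in the randomized year.

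The larger risk is what an analyst may do on reaching this line. The only control scopes in the database will be those done before crossover ESG. If they are used without comment, a contrast between two groups selected after randomization would be reported under a sentence that promises a comparison of treatment arms. Section 7.2.2 does warn that its 24-month %EWL comparison is not one of randomized arms. It gives no such warning for esophagitis.

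Within the ESG arm, the re-scope rule decides whom the esophagitis and durability figures describe. Read as properties of the whole arm, they would be misread if only patients not above 25% EWL supply them.

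**Working it through.** The plan gives no sample size or power for esophagitis, so there is no stated figure to reproduce for this endpoint. Two neighbouring figures do reproduce. The unequal-variance t-test gives 80.1% power at 34 and 51 patients and 90.2% at 45 and 68 (stated: 80% and 90%). The crossover count is 120 × 0.8 × 0.8 = 76.8, stated as at least 77.

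**1. Control data for the test**

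- Control endoscopies scheduled before crossover: 0 of 120 (sections 4.1, 5.3 and 5.6.1.1.3 agree).
- The blank row is not an effect of text extraction: the same row is marked in the ESG Year 1 table and in the crossover table.
- The control row of the 2 × 2 table is 0 and 0. Its expected counts are zero, and the Pearson statistic is undefined.

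**2. Can the pre-crossover scope stand in?**

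- Who has it: only controls who reach 12 months and meet the crossover criteria in 5.5.1.1.1. Section 7.1 expects at least 77 of 120. With the plan's control mean 10 and SD 5, P(EWL ≥ 25) = P(Z ≥ 3) = 0.13%, so on that input the weight-loss filter removes almost nobody and about 120 × 0.8 = 96 remain. Both counts precede the attendance and psychosocial criteria.
- What it measures: prevalence at a first scope. ESG patients are seen at a repeat scope, after an index scope that ruled out contraindications. Section 4.6 counts LA grade C or D esophagitis among these.
- Status: nothing in the plan names it as the comparator.

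**3. How many ESG patients are re-scoped?**

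Under 4.1: 80, or 80 × 0.8 = 64 if the 20% dropout that section 7.1 gives for controls is also assumed for ESG.

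Under 5.5.1.1.2: N × P(EWL ≤ 25), with EWL normal and SD 30 (normality assumed).

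| Mean %EWL | Source | P(EWL ≤ 25) | Of 80 |
|---|---|---|---|
| 25 | section 7.1 | Φ(0) = 0.500 | 40 |
| 48 | 18% TBWL at BMI 40 | Φ(−0.767) = 0.222 | 18 |
| 63 | 18% TBWL at BMI 35 | Φ(−1.267) = 0.103 | 8 |

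The conversion is %EWL = %TBWL × BMI / (BMI − 25): 18 × 40/15 = 48 and 18 × 35/10 = 63. The 18% is the 12-month figure in section 2.2, and the ideal BMI of 25 is from section 2.3. With 20% dropout the first row becomes 32.

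**4. What such numbers can show**

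- Zero esophagitis cases leave an upper 95% limit of 1 − 0.025^(1/n): 8.8% at n = 40, 10.9% at 32, 18.5% at 18 and 36.9% at 8.
- The smallest counts that pass the durability criterion are 29/40 = 72.5% (exact 95% interval 56 to 85%) and 23/32 = 71.9% (53 to 86%). Under 4.1 with dropout it is 45/64 = 70.3% (58 to 81%). The plan attaches no interval to this criterion, so these show precision only.

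**5. The windows.** Section 4.1 gives weeks 48 to 56 and section 5.5.1.1.2 gives weeks 52 to 60; they overlap at 52 to 56.

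**The case against.** *The pre-crossover scope should not be dismissed for falling in Level 2.* This stands. The ESG repeat scope is itself tabulated in the Year 2, Level 2 schedule, and the ESG Year 1 table has no week 52 endoscopy. A reader might infer that the control scope is disqualified by its level; the documents do not support that, since the same argument would remove the ESG scope. The sound grounds are that it is not named as comparator, is a first scope, and reaches only controls selected after randomization.

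*The plan is not really undecided on who is re-scoped.* This largely stands. The detailed procedure and the schedule agree, and the denominator in 4.2.1 is compatible with both. One sentence in the general description is out of line. A reader might infer that the ESG population is wide open; it is better described as one sentence that needs aligning.

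*The count of 40 rests on one input.* This stands. Section 7.1 calls its 25% mean conservative, and the experience cited in section 2.2 points to far fewer. The intervals at 40 and 32 illustrate one scenario.

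*This is one unpowered item in a long secondary list, and reflux is followed elsewhere.* Both arms complete the GERD questionnaire at scheduled visits, and adverse events are collected in both. That limits the weight of the point, but it does not supply endoscopic data for the control side of the test.

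**Conclusion.** The analysis is wrong as written. The esophagitis chi-square has 0 of 120 controls with scheduled data and cannot be run; this rests on the protocol text and schedule alone. The crossover scopes cannot repair it as a randomized comparison.

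The ESG side, under 5.5.1.1.2 and the schedule, consists of patients not above 25% EWL: about 40 of 80 on the plan's inputs, and about 8 to 18 of 80 at 18% TBWL for BMI 40 to 35. These counts assume normality and SD 30, and are before dropout.

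For durability the point is only one of labelling. A reader might infer that the 70% criterion is biased in a known direction. The documents do not support that: 4.2.1 states its denominator openly, and nothing shows how plication scores differ between patients above and below 25% EWL. Nor do they support any effect on the primary endpoint, its power or the SAE threshold. The change should be made because it is cheap and because the present wording invites a selected contrast to be reported as a comparison of arms.

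**What to change.** 1. In 7.2.2, remove esophagitis from the between-arm chi-square.
2. Report it descriptively by LA grade in re-scoped ESG patients, with n and an exact 95% interval, and state that under 5.5.1.1.2 these are patients not above 25% EWL. Where LA grade was recorded at the index endoscopy, show it alongside, so that new findings can be told from existing ones.
3. List pre-crossover control scopes separately, where LA grade was recorded, with no between-arm test.
4. Align the sentence in 4.1 with 5.5.1.1.2 and the Level 2 schedule, on both population and window.
5. Label the durability result as applying to the re-scoped group, with n and interval.

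The cost is a few sentences in 7.2.2, 4.1 and 4.2.1. No endoscopy is added, and the p-value given up could not have been computed. Scoping every control at week 52 would be the alternative. It would add an invasive procedure, and even with all 80 and 120 patients scoped the power would be 51% for assumed rates of 20% against 10% (rates not in the documents), so it is not recommended.
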